1.4 How will the results of this trial be used?

This project addresses the acute developmental and mental health needs of individuals with disabilities, as well as their families, identified by KBHN and CIHR as priority populations. Outcomes will establish the evidence needed to fill an urgent gap in the system –increasing access to treatment for toddlers at the first signs of risk by empowering parents as the agents of change.

In most Canadian jurisdictions, ASD service funding is very difficult to access under age two. Moreover, there is a complete lack of funding/services specific to the needs of toddlers with emerging signs of ASD who do not yet have a confirmed diagnosis. There is a traditional care pathway of generic followed by diagnosis-specific intervention that misses opportunities for more targeted approaches. Similarly, there is a chronic gap, in publicly funded community service models, between early detection and early intervention that does not reflect the state of current evidence (i.e., we can identify the early signs, but despite the existence of evidence-based interventions, there is little that parents can access when initial signs are identified).

Results from this trial will contribute evidence that can be used to make the case for very early intervention as soon as autism-related concerns arise. Exploratory examination of factors related to feasibility and acceptability will inform future implementation work. Our research is embedded in community-based clinical intervention programs, with training partnerships across Canada (e.g., McMaster Children’s Hospital, Children’s Hospital of Eastern Ontario, and Glenrose Rehab Speech-Language services in Alberta) and ongoing collaborations in India (Sethu Centre for Child Development in Goa, as part of the Indo-Canadian Autism Network Symposium; see www.socialabcs.ca for details) and in Israel (in collaboration with The Hebrew University; see www.autismchildfamily.com for details).

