2.8 What are the proposed primary and secondary outcome measures?

Primary Outcome: Toddler vocal responsiveness (blind video-coded).

Secondary Outcomes: 1. *Toddler outcomes:* (a) vocal initiations, (b) social orienting, (c) words understood and used, (d) autism symptoms; 2. *Parent outcomes:* (a) implementation fidelity, (b) self-efficacy, (c) stress.

Exploratory Analyses: 1. *Predictors:* Child factors (e.g., sex assigned at birth, age, baseline language level, ASD symptoms) and parent/family factors that may influence outcomes (e.g., parent gender, parenting role, educational attainment, employment, stress, ethnicity, English spoken at home, family structure)⁴⁰; 2. *Implementation metrics:* Feasibility and acceptability (see below).

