2. **Implementation metrics.** We will measure *acceptability* using our post-treatment Parent Satisfaction Scale²², and a Coaches' Satisfaction Scale (under development) to capture Coaches' perceptions of the adapted model relative to the standard approach. Program *quality metrics* will include evaluation of Coaches' fidelity (based on pre-established video-coding methods). We will examine *participant flow* metrics such as referral sources, ages of children, and number referred, eligible, enrolled, and completed, as well as number of sessions attended/missed/rescheduled.
2. **Sub-group and predictor analyses** will explore child factors (e.g., age, sex, baseline language level) and family factors that are facilitators or barriers to treatment uptake and successful outcomes (e.g., parents' educational attainment, current employment, family structure, parent gender)⁴⁰, using data collected from a Family Profile Form used in our previous work²².
3. **Follow-up (treatment group only).** A 10-minute parent-child interaction video will be collected and coded for toddler responsiveness and parent implementation fidelity using the same procedures as for *time 1* and *time 2*.

2.10 Proposed sample size and justification for assumptions underlying power calculations.

We aim to enroll 120 families into the RCT, across the three participating sites.

This project has two phases, differing only by number of participants and funding source. Specifically, phase 1 (funded by Kids Brain Health Network) involves enrollment of 30 families across the 3 participating sites. For phase 2, funds are being sought through CIHR (to be adjudicated in March 2021). If funded, we will submit an amendment to increase recruitment up to 100. The proposed sample ($n = 100$; ~50 per treatment arm) will yield 80% power to detect a medium effect (at alpha = .05)⁴¹. The assumption of a medium effect comes from our previous RCT which yielded $R^2 = .43$ for the same primary outcome²². We will over-sample by 20% (i.e., recruit to $n = 120$) to allow for attrition (see 2.14). Given that this is an individually randomized group treatment trial (with 1 group-based and 1 individually administered arm) analyses will account for the intra-class correlations associated with group participation, as recommended³⁴. If Phase 2 is not funded, we will use data from Phase 1 as pilot data for further funding applications.

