2.16 What is the proposed type of analyses?

The primary analysis will yield a comparison of rates of toddler vocal responsiveness between the two conditions, controlling for the variables described above. The statistical model for the

Primary Outcome will be either a Poisson or negative binomial regression (if there is overdispersion of the counts), using the number of prompts and/or time as offsets and applying the appropriate correlation structure for observations by participant, and controlling for intraclass correlation due to clustering. Growth curve analysis will be used to calculate the trajectory of change in responsive vocalizations over time for each person based on whatever data are available (if at least 2 measurements), and then estimates (imputes) the missing data if the person followed the same trajectory. Otherwise, a worst-case (no vocal response) scenario can be used.

Secondary Outcomes: We will analyze as per the primary outcome for count variables (e.g., video-coded toddler initiations). We will use repeated measures ANOVA or Generalized Estimating Equations for scores (e.g., word inventory, ASD symptoms, parent efficacy, stress).

Exploratory Analyses: (1) *Predictors* of primary and secondary outcomes will first be assessed univariately for their effect on the outcomes, and significant factors will be subjected to multivariate analysis using the appropriate regression model. We will examine the influence of sex (toddlers), parent gender, and parenting roles by entering these factors as covariates. Given that sample size calculations are not done for all these factors, these analyses are exploratory. (2) *Implementation metrics* (feasibility, acceptability) will be examined descriptively.

[figure not shown]
2.17 Proposed frequency of analyses. Analyses will be conducted at two time points: (1) following the end of Phase 1 ($n = 30$), and (2) at the end of the larger trial ($n = 100$).

2.18 Planned subgroup analyses.

Subgroup analyses, run separately for treatment and control groups, will explore effects of: (1) sex: *Do outcomes differ for boy vs. girl toddlers?*; (2) gender: *Are there differences in parent fidelity and self-efficacy based on self-identified parent gender?*; (3) baseline language functioning: *Do outcomes differ for toddlers who begin the program below (vs. at or above) a 12-month language level (based on parent-reported CDI scores)?*

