2.19 Has any pilot study been carried out using this design?

We have made *two substantive adaptations to the standard Social ABCs program*, each with some pilot data. First, we developed a **Group-based** protocol for didactic learning and shortened the duration of 1:1 coaching (6 vs. 12 weeks). We have pilot tested the Group adaptation ($n = 45$ in-person families) with positive reports from families and Coaches (see *Report to Alva Foundation*, attached). Preliminary analyses⁴³ reveal significant gains in toddler responsiveness and parent fidelity comparable to those for the original model (see Fig. 1 and 2). Unique to the Group model is evidence of **reduced parenting stress** (Fig 3), which highlights the enhanced clinical impact of a Group-based intervention that goes beyond increased efficiency²⁸. Parents in the Group model also reported improved toddler language (words understood and spoken³⁸ significantly increased, p 's $< .001$), reduced toddler autism symptoms (APSI³⁷ scores decreased significantly from 20.5 to 17.2; $p = .0005$), and high satisfaction (33.1 out of a possible 35).

The second key adaptation to our original model involved developing a **virtual coaching protocol** for the Group model. Our team made this additional adaptation in April 2020, in response to the Covid-19 pandemic, *and we have already piloted this adapted virtual Group model with an additional 22 families (and 11 in progress)*, demonstrating the feasibility and promise of this novel approach. Preliminary analyses of the **virtual Group-based adaptation** reveal outcomes similar to the *in-person Group model*, with comparable gains in parent fidelity (from 30.8% to 72.2%; $p = .009$) and a trend toward reduced parenting stress (from 31.8 to 25.5) similar in magnitude to the in-person values. Although child-level video data have not yet been coded, parent-reported autism symptoms (on the APSI³⁷) decreased significantly (23.2 to 18.5; $p = .004$), and satisfaction was high (32.5 out of 35). Parent-reported toddler language also increased (p 's = .003, .018, respectively for words understood and spoken). ***On all metrics evaluated to date, changes are commensurate across in-person and virtual delivery methods.***

The **adapted, virtual group delivery model** is a promising, innovative and cost-efficient way to provide intervention to toddlers with probable or confirmed autism at the first signs of concern.

3. Trial Management

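### Section 2.16 names no between-arm contrast for the score secondaries; fixing Time 1 adjusted for Time 0 would avoid a diluted test at almost no cost

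*Protocol*

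**What the plan says.** Section 2.9 ties the primary outcome to one contrast, the change in toddler vocal responsiveness from Time 0 to Time 1. Section 2.8 lists four toddler secondaries ("a) vocal initiations, (b) social orienting, (c) words understood and used, (d) autism symptoms") and three parent secondaries: implementation fidelity, self-efficacy and stress.

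Section 2.16 divides the secondaries by type. Count variables are analysed in the same way as the primary. For the others it says "We will use repeated measures ANOVA or Generalized Estimating Equations for scores (e.g., word inventory, ASD symptoms, parent efficacy, stress"). No visit, model term or baseline adjustment is given for these scores.

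Three other sections bear on which visits could enter:

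- Section 2.1 has three components: a parallel-group comparison, an own-control analysis of Arm B once it has been treated, and a growth curve for the treatment group over Times 0, 1 and 2.
- Section 2.2 offers Arm B families the program once the control phase is over, and gives both arms the same data collection and time points.
- Section 2.7 schedules data for both groups at Times 0, 1 and 2.

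**The concern.** A repeated-measures ANOVA or a GEE model yields several tests, and they answer different questions. The arm main effect averages over every visit entered. The arm-by-time test asks whether the arms follow different courses over those visits. A baseline-adjusted comparison at Time 1 asks what the parallel-group part of the design was built to answer.

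The choice matters here because the arms are treated differently only between Time 0 and Time 1. At Time 0 neither arm has been treated. At Time 2, Arm A has finished and Arm B has been offered the same program. A main effect therefore averages the one informative visit with visits where little or no difference is expected. At stake is a real benefit on word inventory, autism symptoms, parent self-efficacy or stress that the chosen test is too weak to show.

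**Working it through.** **The plan's own figure.** Section 2.10 says that about 50 per arm "will yield 80% power to detect a medium effect (at alpha = .05"). That statement rests on the previous trial's primary outcome; the protocol gives no power for the secondaries. Reading medium as d = 0.5, an unadjusted comparison of 50 v 50 has z = 0.5/√(2/50) = 2.50. Power is Φ(2.50 − 1.96) = 0.705 two-sided and 0.804 one-sided. The stated 80% is thus reached only one-sided on this reading (a regression reading, f² = 0.15 with six predictors, gives 0.81). That is a separate matter; d = 0.5 and 50 per arm are borrowed here only as a common yardstick.

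**Inputs**

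- 50 per arm: section 2.10, so the variance factor is k = 2/50 = 0.04.
- Two-sided alpha of .05: the .05 is from section 2.10, the sidedness is assumed.
- Standardized difference of 0.5 at Time 1: assumed.
- Correlation ρ between any two visits: assumed 0.5, range 0.3 to 0.7.
- Arm B has caught up at Time 2: assumed. The arm differences at Times 0, 1, 2 are then (0, 0.5, 0).
- Unit variance at each visit; clustering ignored.

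**Formulas, with ρ = 0.5 put in**

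1. Time 1 adjusted for Time 0: variance k(1 − ρ²) = 0.04 × 0.75 = 0.03; z = 0.5/√0.03 = 2.887; power Φ(0.927) = 0.82, or 0.81 to 0.82 with the t distribution or by simulation.
2. Two-visit arm-by-time (equivalent to comparing change scores): variance k × 2(1 − ρ) = 0.04; z = 2.50; power 0.70.
3. Two-visit main effect: the effect halves to 0.25; variance k(1 + ρ)/2 = 0.03; z = 1.443; power 0.30.
4. Three-visit main effect: effect 0.5/3 = 0.167; variance k(1 + 2ρ)/3 = 0.0267; z = 1.021; power 0.18.
5. Three-visit arm-by-time (F test, 2 and 196 df): deviations of (0, 0.5, 0) from their mean have sum of squares 0.1667; noncentrality 0.1667/[k(1 − ρ)] = 0.1667/0.02 = 8.33; power 0.73.

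**Range over the assumed correlation** (same formulas; t or F distribution)

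| Test | ρ = 0.3 | ρ = 0.5 | ρ = 0.7 |
|---|---|---|---|
| Time 1 adjusted for Time 0 | 0.74 | 0.82 | 0.93 |
| Three-visit arm-by-time | 0.57 | 0.73 | 0.92 |
| Two-visit arm-by-time | 0.55 | 0.70 | 0.89 |
| Two-visit main effect | 0.34 | 0.30 | 0.27 |
| Three-visit main effect | 0.20 | 0.17 | 0.15 |

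Simulation put the last row at 0.18 for ρ = 0.5.

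**If Arm B does not catch up at all**, the differences are (0, 0.5, 0.5). The three-visit main effect then has z = (1/3)/√0.0267 = 2.04 and power of about 0.53. The three-visit arm-by-time power does not change, because the deviations again have sum of squares 0.1667.

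Baseline-adjusted Time 1 is the strongest in every column. Its lead over the arm-by-time tests is clear at ρ = 0.3 and small at ρ = 0.7. Its lead over the main effects is large throughout.

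**The case against.** The strongest objection is that the score outcomes may have no third visit in Arm A. Section 2.2 places questionnaires at baseline and after the intervention, and mentions only a video at follow-up. Section 2.9 describes follow-up as treatment group only, by video, for responsiveness and fidelity. Section 2.7 gives Arm A's Time 2 the purpose of maintenance in those same two measures. Section 2.1 also keeps the parallel-group, own-control and growth-curve parts apart. On this reading the three-visit figures describe data that will not exist. That is a fair reading but not the only one, since section 2.7 says without qualification that both groups provide data at all three times. It also does not remove the point: with two visits the stated method gives about 0.70 or 0.30, against about 0.81.

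A second objection is that the exact contrast for a secondary outcome is usually settled in the SAP, which is not at hand. This stands to the extent that the gap is not an error that undermines the trial. But section 2.16 does specify the score analysis, and what it specifies admits a poor comparison.

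A reader might also infer more than the documents support:

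- **That no secondary has a fixed contrast.** Count secondaries are analysed like the primary, whose contrast is Time 0 to Time 1.
- **That the secondaries form an uncontrolled family with a false benefit in about one null trial in four.** There is one primary, no secondary is called confirmatory, and .05 appears only in the power statement. The figure of about 25% (eight tests, two-sided, correlation 0.5) counts errors in both directions. In the favourable direction it is about 12.5%, and about 18% if the tests are independent. Any hierarchy among secondaries belongs in the SAP.
- **That the secondaries are efficacy claims** because the predictor analyses are called exploratory ("Given that sample size calculations are not done for all these factors, these analyses are exploratory") or because of the pilot remark on stress in section 2.19. The first only labels the predictors, and the second is background that sets no decision rule.
- **That fidelity is wrongly classed.** Section 2.13 already treats it as an index of skill acquisition; listing it as a secondary is a matter of preference.

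**Conclusion.** The point holds for the four outcomes that section 2.16 names as scores: word inventory, autism symptoms, parent self-efficacy and stress. The between-arm contrast is open, and some of the tests that the named methods produce suit this delayed-access design badly. With d = 0.5, 50 per arm and ρ = 0.5, choosing an arm-by-time test over baseline-adjusted Time 1 costs roughly 8 to 11 percentage points of power (0.81 v 0.73 or 0.70). Choosing a main effect costs roughly 50 to 60 points (0.81 v 0.30 or 0.18).

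These sizes rest on the assumed effect, correlation and catch-up, and they ignore clustering, which would lower the absolute powers. The ranking held across the correlations tried. The documents do not show that a main-effect test is intended, or that the contrast would be chosen after seeing results. This is therefore a nearly free improvement, not a flaw in the primary analysis.

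**What to change.** In section 2.16, state that each score secondary is compared between arms at Time 1, adjusted for its own Time 0 value and allowing for clustering by intervention group, as section 2.10 already intends. State that Time 2 is left out of the between-arm test and serves only the own-control and maintenance analyses of section 2.1. It would also help to say in section 2.7 whether questionnaires are collected at Time 2 in both arms, so that it agrees with sections 2.2 and 2.9.

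The cost is a few sentences. No new data, visits or participants are needed, because Time 0 and Time 1 scores are already collected in both arms. The only thing given up is the freedom to choose among repeated-measures tests later.

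### Section 2.18 runs the subgroup analyses separately in each arm, so they neither estimate nor test whether the treatment effect differs by subgroup

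*Protocol*

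**What the plan says.** Protocol section 2.18 fixes the method: "Subgroup analyses, run separately for treatment and control groups, will explore effects of" three factors. Its questions are:

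- toddler sex: "Do outcomes differ for boy vs. girl toddlers";
- parent gender: "Are there differences in parent fidelity and self-efficacy based on self-identified parent gender";
- baseline language: "Do outcomes differ for toddlers who begin the program below (vs. at or above) a 12-month language level".

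Section 2.16 handles some of the same factors in another way: "We will examine the influence of sex (toddlers), parent gender, and parenting roles by entering these factors as covariates". That is main-effect adjustment. Other predictors are screened one at a time, and the significant ones go into a multivariable model. Section 2.16 also gives the status of this work: "Given that sample size calculations are not done for all these factors, these analyses are exploratory".

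The purpose is in section 2.9, where the sub-group and predictor analyses are to explore child factors and "family factors that are facilitators or barriers to treatment uptake and successful outcomes".

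The protocol mentions no arm-by-subgroup interaction and no between-arm comparison within a subgroup.

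**The concern.** The method in 2.18 does not match the purpose in 2.9. Whether a factor helps or hinders the success of treatment is a question about differences in treatment effect. Comparing boys with girls inside one arm gives the association of sex with outcome in that arm. Such an association may be purely prognostic: toddlers with more language at baseline may respond more to prompts later whichever arm they are in.

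Splitting by arm also removes the randomised comparison from each subgroup. As planned, the trial would give no estimate of benefit for toddlers below the 12-month language level, for example.

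At stake is what the report can say about who benefits. With two sets of within-arm results and nothing linking them, the obvious shortcut is to compare significance across arms, and that is not a test of effect modification.

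This is not a detail left to a statistical analysis plan. The protocol itself fixes the separate-by-arm approach, and an analysis plan that followed it would inherit the gap.

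**Working it through.** **Plan's own figure.** The protocol states no power or effect size for subgroups, so there is none to reproduce.

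**What is estimated.** Let D_T be the subgroup difference in mean outcome in the treatment arm and D_C the same difference in the control arm. Section 2.18 yields D_T and D_C separately. The difference in treatment effect between subgroups is D_T − D_C, and the plan never forms or tests it.

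**Inputs.**
- About 50 per arm analysed (section 2.10).
- Two-sided 5% test within each arm (section 2.10 gives alpha .05; the sidedness is assumed).
- Subgroup shares of 50/50, 70/30 and 80/20 (assumed; the protocol gives none).
- A true subgroup difference d in SD units, equal in both arms, so that there is no effect modification (assumed).
- Independent observations, with no clustering by parent group (a simplification).

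**Within-arm comparison.** With n1 and n2 in the two subgroups of one arm, the standard error in SD units is √(1/n1 + 1/n2).
- 25/25: √(1/25 + 1/25) = 0.283
- 35/15: √(1/35 + 1/15) = 0.309
- 40/10: √(1/40 + 1/10) = 0.354

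Let p be the power of the within-arm t-test (noncentral t, 48 degrees of freedom, noncentrality d/SE). The arms are independent, so the treatment arm alone is significant with probability p(1 − p), and exactly one arm, either way, with probability 2p(1 − p). For d = 0.5:

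| Split | p | Treatment arm alone | Exactly one arm |
|---|---|---|---|
| 25/25 | 0.410 | 0.410 × 0.590 = 24% | 48% |
| 35/15 | 0.355 | 0.355 × 0.645 = 23% | 46% |
| 40/10 | 0.283 | 0.283 × 0.717 = 20% | 41% |

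Other values of d, exactly one arm significant (25/25 and 40/10):
- d = 0: 9.5% and 9.5%
- d = 0.3: 30% and 23%
- d = 0.8: 33% and 48%

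A simulation of 20,000 trials per scenario at 25/25 agreed: 10%, 29%, 48% and 33% for d = 0, 0.3, 0.5 and 0.8. The interaction test rejected in about 5% throughout, as it should.

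**After the change.** The standard error of D_T − D_C is √2 times the within-arm one. Using the normal approximation, power for a true interaction of 0.5 SD is Φ(0.5/SE − 1.96) + Φ(−0.5/SE − 1.96), and the interaction detectable with 80% power is 2.80 × SE.

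| Split | SE of interaction | Power at 0.5 SD | Detectable at 80% |
|---|---|---|---|
| 50/50 | 0.400 | 24% | 1.12 SD |
| 70/30 | 0.436 | 21% | 1.22 SD |
| 80/20 | 0.500 | 17% | 1.40 SD |

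**The case against.** The strongest reply is that the three questions in 2.18 ask whether outcomes differ, and within-arm contrasts answer that. The protocol never says it will test moderation. This stands. A reader might infer that 2.18 fails to answer its own questions, or that the protocol sets out to identify who benefits more. The text supports neither reading. The gap is narrower and lies between the method in 2.18 and the purpose in 2.9.

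Even that purpose needs care. In "facilitators or barriers to treatment uptake and successful outcomes" the word treatment is attached to uptake. For uptake of the coached programme an interaction with arm has no meaning, because only Arm A receives it during the randomised comparison. The point applies only to successful outcomes, so far as these mean success of treatment.

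A reader might also take the 24% and 48% as the plan's false-positive rates for moderation. They are not. They show how often comparing significance across arms would mislead, and the protocol plans no such comparison. The larger figure counts disagreement in both directions, while the feared pattern, significant under treatment but not under control, is about half of it. Both rest on assumed shares and effect sizes.

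Finally, the analyses are already exploratory and do not touch the primary comparison. This limits the harm. It does not make a within-arm contrast answer a question about treatment effects.

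**Conclusion.** The point holds in a limited form. As written, section 2.18 can describe subgroup differences in outcome within each arm. It cannot support any statement that the benefit of treatment differs by toddler sex, parent gender or baseline language, and nothing elsewhere in the protocol fills the gap.

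The size is illustrative. With an equal 0.5 SD subgroup difference in both arms and no interaction, the treatment arm alone is significant in about 20% to 24% of trials, and the arms disagree in about 41% to 48%. These figures assume 50 analysed per arm, two-sided 5% tests, splits from 80/20 to 50/50 and no clustering. The conclusion about what is estimated depends on none of these assumptions.

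It should be corrected because the protocol fixes the method and the change is small. It does not threaten the primary result.

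**What to change.** In section 2.18, replace the separate-by-arm clause with one model fitted to both arms, containing arm, the subgroup factor and their interaction. Use the model that belongs to each outcome: the Poisson or negative binomial model for vocal responsiveness, the repeated measures ANOVA or GEE for scores such as self-efficacy, and fidelity's own model for fidelity. Putting every factor into the primary model would not do, because the parent-gender question concerns fidelity and self-efficacy.

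Report the between-arm effect in each subgroup and the interaction, each with a 95% confidence interval. Within-arm summaries may stay as description, and the 12-month language cut may be kept.

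No new data are needed and the edit is a sentence or two. The cost is imprecision. At n = 100 the power for a 0.5 SD interaction is about 17% to 24%, and clustering would lower it further. The text should therefore keep the results exploratory and say that a non-significant interaction is not evidence that the treatment effect is the same across subgroups.
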